3.2 Analysis Populations

Modified Intent-to-treat (mITT) Population: Modified Intent-to-treat (mITT) Population is defined as all subjects who receive at least 1 dose of study medication.

The mITT Population will be used for tables of demography, baseline characteristics and efficacy analyses.

Safety: The safety population is defined as all subjects who receive at least one dose of study medication. In this study, safety population is equivalent to mITT population.

3.3 Subject Disposition and Evaluability

Subjects with screen failure (i.e., subjects who signed the informed consent were screened but never started the study treatment, their basic demographics and any AE after signing the informed consent may have been collected in the CRF) will be excluded from any populations defined in section 3.2, therefore these subjects will be excluded in any summary tables or listings.

The number of subjects discontinuing from the study and the primary reason for discontinuation will be summarized.

3.4 Protocol Deviations

All protocol deviations will be identified and classified as major or minor (as defined below) before the clinical database lock, and will be presented in a listing.

Major Deviation: Protocol deviation that may impact the accuracy, and/or reliability of the study data or that may impact subject rights, safety or well-being.

Minor Deviation: Protocol deviation that does not impact the accuracy, and/or reliability of the study data or subject rights, safety or well-being.

Serious non-compliance: Serious non-compliance presents a significant risk to the safety of study patients or significantly affects the scientific value of the reported results of the study. This classification may include fraud, scientific misconduct and serious breaches of ethical conduct. Persistent clinical investigator site noncompliance, even if not serious, is also considered within this definition.

3.5 Demographics and Baseline Characteristics

3.5.1 Demographics

Subject demographics and baseline characteristics will be summarized for the mITT population. Descriptive statistics will be provided for age, height, weight, and body mass index (BMI). Frequencies and percentages will be tabulated for sex, race, and ethnicity.

3.5.2 Medical History

Medical history will be summarized by primary system organ class and preferred term. Medical history will be coded using Medical Dictionary for Regulatory Activities (MedDRA, Version 20.1 or higher) terminology.

3.6 Prior and Concomitant Medications

Concomitant medications will be coded using WHO Drug Dictionary. Prior medications are those that started and stopped before the start of study treatment; concomitant medications are all medications taken after the start of study treatment, during each study period, including those started before but ongoing at the start of study treatment. Where a medication start date is partially or fully missing, and it is unclear as to whether the medication is prior or concomitant, it will be assumed that it is concomitant.

Number and percentage of incidence of prior and concomitant medication will be summarized according to ATC class and preferred drug name.

3.7 Treatment Compliance and Exposure

The duration of exposure is defined as,

$$\text{Duration of exposure (days)} = \text{Date of last dose} - \text{Date of Study Day 1} + 1.$$

The descriptive summary statistics of the treatment duration will be presented.

3.8 Efficacy Analysis

3.8.1 Primary Endpoint

- The number (%) of subjects with a 75% decrease in PASI by Week 16
In addition to the descriptive statistics (n, %, CI) for each group, the difference of the percentage of subjects with a 75% decrease in PASI by Week 16 between each treatment and control group will be analyzed with Fisher's exact method.

Patients without Week 16 assessment will be counted as failed to reach 75% decrease.

3.8.2 Secondary Endpoints

- The Week 16 change from baseline in PASI scores
The descriptive statistics (n, mean, 95% CI) of Week 16 change from baseline in PASI scores will be summarized and tabulated by treatment groups.
- The Week 16 percent change from baseline in PASI
The descriptive statistics (n, mean, 95% CI) of Week 16 percent change from baseline in PASI scores will be summarized and tabulated by treatment groups.
- Improvements in PGA of “clear” or “almost clear” (excellent) at Week 16
Use the same approach with primary endpoint analysis in section 3.8.1.
- Improvements in DLQI at Week 16
The descriptive statistics (n, mean, 95% CI) of DLQI changes from baseline to Week 16 will be summarized and tabulated by treatment.
- The Week 48 change from baseline in PASI scores
The descriptive statistics (n, mean, 95% CI) of Week 48 change from baseline in PASI scores will be summarized and tabulated by treatment groups.
- The Week 48 percent change from baseline in PASI
The descriptive statistics (n, mean, 95% CI) of Week 48 percent change from baseline in PASI scores will be summarized and tabulated by treatment groups.
- The Week 48 change from Week 16 in PASI scores
The descriptive statistics (n, mean, 95% CI) of Week 48 change from Week 16 in PASI scores will be summarized and tabulated by treatment groups.

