### **5.5 Study Endpoints**

The primary safety endpoint will be the percentage of subjects in each treatment group experiencing AEs.

The primary efficacy endpoint for analyses will be the number (%) of subjects with a 75% decrease in PASI by Week 16.

The secondary efficacy endpoints for analysis will include the following:

- A 50% reduction in Week 16 PASI score (PASI 50)
- The mean Week 16 percent change from baseline in PASI
- Improvements in PGA of “clear” or “almost clear” at Week 16
- Improvements in DLQI at Week 16

The exploratory efficacy endpoint is:

- To evaluate the concentration and changes in IL-17 expression in blood, tissue, and other biomarkers in punch biopsy after 16 weeks of dosing with KD025

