### 6.2 Inclusion Criteria

To be eligible for participation in the study, each subject must meet all of the following criteria:

1. Adult, between the ages of 18 and 65 years
2. Able to provide written ICF prior to the performance of any study specific procedures
3. A diagnosis of moderate to severe chronic plaque psoriasis and is a candidate for systemic therapy or phototherapy
4. A PASI of  $\geq 12$  at screening and prior to the first dose of study drug, confirmed at Week 1 (Day 1)
5.  $\geq 10\%$  PASI body surface area involvement at screening and prior to the first dose of study drug, confirmed at Week 1 (Day 1)
6. Willing to avoid tanning devices
7. Adequate bone marrow function
  - a. Absolute neutrophil count (ANC)  $> 1500/\text{mm}^3$
  - b. Hemoglobin  $> 9.0 \text{ g/dL}$
  - c. Platelets  $> 100,000/\text{mm}^3$
8. Adequate safety laboratory values
  - a. Serum total bilirubin within normal limits (WNL)
  - b. AST and ALT  $< 2 \times$  upper limit of normal (ULN)
  - c. Serum creatinine  $< 1.5 \times$  ULN
9. Female subjects of childbearing potential have a negative pregnancy test at screening.  
Females of childbearing potential are defined as sexually mature women without prior

hysterectomy or those who have had any evidence of menses in the past 12 months.

However, women who have been amenorrheic for 12 or more months are still considered to be of childbearing potential if the amenorrhea is possibly due to prior chemotherapy, anti--estrogens, or ovarian suppression.

- Women of childbearing potential (i.e., menstruating women) must have a negative urine pregnancy test (positive urine tests are to be confirmed by serum test) documented within the 24-hour period prior to the first dose of study drug.
  - Sexually active women of childbearing potential enrolled in the study must agree to use 2 forms of accepted methods of contraception during the course of the study and for 3 months after their last dose of study drug. Effective birth control includes (a) intrauterine device plus one barrier method; (b) on stable doses of hormonal contraception for at least 3 months (e.g., oral, injectable, implant, transdermal) plus one barrier method; (c) 2 barrier methods. Effective barrier methods are male or female condoms, diaphragms, and spermicides (creams or gels that contain a chemical to kill sperm); or (d) a vasectomized partner.

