### **12.7 Efficacy Analysis**

The primary efficacy endpoint for analyses will be the number (%) of subjects with a 75% decrease in PASI by Week 16.

The secondary efficacy endpoints for analysis will include the following:

1. A 50% reduction in Week 16 PASI score (PASI 50)
2. The mean Week 16 percent change from baseline in PASI
3. Improvements in PGA of “clear” or “almost clear” at Week 16
4. Improvements in DLQI at Week 16

The exploratory efficacy endpoints are:

- To evaluate the concentration and changes in IL-17 expression in blood, tissue, and other biomarkers in punch biopsies after 16 weeks of dosing with KD025

Efficacy analyses will be divided into 2 periods: the double-blind treatment period through database lock at Week 16 and the open-label, 32-week continuation period.

Efficacy analyses will include the number (%) of subjects with a 75% decrease in PASI (number of subjects that reach PASI 75) at Week 16 in the KD025 treatment groups compared with the placebo group in a pairwise manner using a Fisher’s Exact test. The number of subjects who reach PASI 50 at Week 16 will be analyzed similarly. Treatment group differences in DLQI and PGA changes from baseline to Week 16 will be assessed using an analysis of covariance (ANCOVA) model with treatment as a fixed effect and a subject’s baseline value as a covariate.

No adjustments for multiplicity are being made for this Phase 2 study.

For further details, see the statistical analysis plan (SAP).

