3.1.2 General Considerations

General considerations for descriptive statistics and presentation for continuous and categorical data are given below.

Continuous data will be described using descriptive statistics: number of observations (n), mean, standard deviation, median, minimum and maximum. Frequencies and percentages will be used for summarizing discrete (categorical) data. When categorical data are presented, the percent will be suppressed when the count is zero in order to draw attention to the nonzero counts. The denominator for all percentages, unless otherwise specified, will be the number of subjects in the cohort or in the specified analysis population.

Means, medians, standard deviations, and confidence intervals (CI) will be reported to one decimal place more than the data reported on the CRF or by the vendor. Minimum and maximum will be reported to the same number of decimal places displayed on the CRF or by the vendor. P-values will be reported to 4 decimal places.

Efficacy analysis will be performed on blinded period and entire treatment duration. Safety analysis will be performed on blinded period, open-label period and entire treatment duration.

Unless otherwise indicated, all summary tables for blinded period and entire treatment duration will be presented by the following groups: cohort 1, cohort 2,

cohort 3, cohort 4, cohort 5, and all KD025. For open-label period, summary tables will be presented by the actual dose group (400 mg KD025 QD for all subjects).

Because of the exploratory nature of the study, no adjustments will be made for the multiplicity of endpoints.

Last Observation Carried Forward (LOCF) method will be incorporated when applicable.

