3.14 Primary CSR Analysis

A primary CSR analysis will be conducted after conclusion of the study.

4 List of Tables, Figures and Listings

In all tables, figures and listing, results will be presented by treatment cohorts and overall, unless be otherwise specified.

Table 2: Demographics and Baseline Characteristics TLFs

T/F/L	Title	Population
T	Subject disposition	mITT
L	Subject disposition	mITT
L	Protocol deviations	mITT
T	Demographics and baseline characteristics	mITT
L	Demographics and baseline characteristics	mITT
T	Medical histories by primary system organ class and preferred terms	mITT
L	Medical history	mITT

Table 3: Efficacy TLFs

T/F/L	Title	Population
PASI		
T	The number (%) of subjects with a 75% decrease in PASI by Week 16	mITT
T	The number (%) of subjects with a 75% decrease in PASI by Week 48	mITT
T	PASI score, change and % change from baseline by visit	mITT
T	PASI change and % change from Week 16 to Week 48 visit	mITT
PGA		
T	The number (%) of subjects with “clear” and “almost clear” (excellent) in PGA at Week 16, 48	mITT
DLQI		

T/F/L	Title	Population
T	DLQI score, change and % change from baseline by visit	mITT
Exploratory Endpoints		
T	Descriptive statistics for IL-17 by visit	mITT

Table 4: Safety TLFs

T/F/L	Title	Population
T	Concomitant medications	mITT
L	Concomitant medications	mITT
T	Treatment exposure and compliance	mITT
L	Treatment exposure and compliance	mITT
T	Dose modifications and interruption	mITT
L	Dose modifications and interruption	mITT
T	Overall summary of TEAEs	Safety
T	TEAEs by Soc/PT	Safety
T	TEAEs by PT	Safety
T	TEAEs by severity and PT	Safety
T	Treatment related AEs by PT	Safety
T	Serious TEAEs by Soc/PT	Safety
T	Serious TEAEs by PT	Safety
T	Treatment related SAEs by PT	Safety
T	Grade 3-5 TEAEs by Soc/PT	Safety
T	Grade 3-5 TEAEs by PT	Safety
T	Treatment related grade 3-5 AEs by Soc/PT	Safety
L	AEs	Safety
L	AE Leading to treatment discontinuation	Safety
L	Death	Safety
T	Lab values and their change from baseline	Safety
F	Lab values by visit	Safety
T	Shifts in CTC grade from baseline to highest grade post-baseline of laboratory	Safety
L	Lab values with CTC grade ≥ 3	Safety

T	Vital signs and their change from baseline	Safety
L	Vital signs	Safety
T	ECG parameters and their change from baseline	Safety
F	ECG parameters by visit	Safety
T	Number and percentage of subjects with QTcF by visit a) absolute ranges and b) change from baseline	Safety
T	QTcF abnormalities	Safety
L	ECG values	Safety

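### No KD025-versus-placebo estimate is prespecified for Week 16 PASI change or percent change; both are only summarised arm by arm

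*SAP*

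**What the plan says.** **The endpoints.** Protocol 5.5 and 12.7 list "The mean Week 16 percent change from baseline in PASI" as a secondary efficacy endpoint. Absolute and percent change at Week 16 are both secondary objectives (protocol 5.2, SAP 2.1.2).

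**Their analysis.** For absolute change, SAP 3.8.2 states: "The descriptive statistics (n, mean, 95% CI) of Week 16 change from baseline in PASI scores will be summarized and tabulated by treatment groups". Percent change is handled the same way: "Week 16 percent change from baseline in PASI scores will be summarized and tabulated by treatment groups". The efficacy table list (SAP section 4, Table 3) has one matching by-visit output, "PASI score, change and % change from baseline by visit", and its title mentions no contrast.

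**Columns of the tables.** SAP 3.1.2 presents blinded-period tables for cohorts 1 and 2, then "cohort 3, cohort 4, cohort 5, and all KD025". Cohort 5 is placebo (SAP 2.2, Table 1).

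**Endpoints that do get a contrast.** In SAP 3.8.1 the PASI 75 difference "between each treatment and control group will be analyzed with" Fisher's exact method, and SAP 3.8.2 applies the same approach to PGA. Protocol 12.7 says: "Treatment group differences in DLQI and PGA changes from baseline to Week 16 will be assessed using an analysis of covariance". It names Fisher's test for PASI 75 and PASI 50, gives no method for PASI change or percent change, and refers to the SAP for details.

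**Entry and baseline.** Protocol 6.2, criterion 4, requires PASI of at least 12 at screening and again on Day 1. Baseline is the last value before the first dose (protocol 12.1, SAP 3.1.4).

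**The concern.** The trial is randomised and placebo-controlled, and PASI change is its main continuous measure of disease. The question for that measure is how far each KD025 cohort differs from placebo. A per-arm mean with its CI answers a different question: whether that arm changed from baseline. Everyone enters above a PASI threshold and every arm can show a placebo response, so part of any within-arm fall has nothing to do with drug.

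The plan leaves the between-arm estimate to whoever reads the table. That estimate would be post hoc, without baseline adjustment, and open to choice of visit, scale and missing-data rule. The gap matters more because enrolment ended at 110 (SAP 3.12), about 22 per cohort, where the planned responder comparison is weak. In the SAP, the only efficacy outcomes formally compared with placebo are dichotomised ones.

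**Working it through.** **1. Set the endpoints side by side.**

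| Week 16 endpoint | Protocol 12.7 | SAP 3.8 | Placebo contrast planned? |
|---|---|---|---|
| PASI 75 | Fisher | Fisher v control | Yes |
| PGA | ANCOVA | Fisher v control | Yes |
| DLQI | ANCOVA | Descriptive only | Protocol only |
| PASI change | No method | Descriptive only | No |
| PASI percent change | No method | Descriptive only | No |

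**2. The plan's own power figure.** SAP 3.12 gives about 85% for PASI 75 with 30 evaluable per arm, 33% v 5%, two-sided 5%, Fisher's exact test. Exact enumeration of that test gives 73.1%; an arcsine approximation gives 84.9%. This mismatch is a separate matter and nothing below depends on it. The documents give no power figure for PASI change.

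**3. The responder comparison at the actual size.** 110 / 5 = 22 per arm. With the SAP's 17% without a Week 16 score, 22 × 0.83 = 18.3, so about 18. Exact Fisher power at 33% v 5% is 59.5% at 22 per arm and 46.4% at 18.

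**4. A comparison of mean change.** The documents give no SD for PASI change, so effects are in SD units. The half-width of the 95% CI for a difference is t(0.975, 2n − 2) × √(2/n):
- n = 22: 2.018 × √(2/22) = 0.61 SD
- n = 18: 2.032 × √(2/18) = 0.68 SD

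Two-sample t-test power, two-sided 5%, 22 per arm: 49.4% at 0.6 SD and 73.6% at 0.8 SD. Any gain from baseline adjustment is not counted, because the documents give no correlation.

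**5. The upper end.** Assume percent improvement is normal with equal SD in both arms. The SAP's PASI 75 rates then fix the standardised difference: d = z(0.95) − z(0.67) = 1.645 − 0.440 = 1.205. Power is 97.4% at 22 per arm and 94.0% at 18.

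The assumption is strained, because improvement cannot exceed 100%. Suppose mean placebo improvement is m (an assumption, range 10% to 30%), so SD = (75 − m) / 1.645:
- m = 10: SD = 39.5, mean difference 1.205 × 39.5 = 47.6 points, KD025 mean 57.6, and 14% of the KD025 arm above 100%.
- m = 30: SD = 27.4, mean difference 33.0 points, KD025 mean 63.0, and 9% above 100%.

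**6. What the entry threshold contributes.** Simulation with no drug and no placebo effect, selecting PASI of at least 12 at two visits and following up at a third. Assumed inputs, none from the documents: population mean/SD 14/6 and 18/7, between-visit correlation 0.6 to 0.9.
- Mean change: −0.15 to −1.04 points. Mean percent change: +0.1% to −3.6%.
- Within-arm 95% CI (n = 22) wholly below zero: 4% to 15% of arms for change and 3% to 10% for percent change, against a nominal 2.5%.
- Between-arm contrast: rejects in 4.7% to 5.2% of null trials, so it removes the artefact.

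**7. What a reader can recover.** From the printed n, mean and CI limits: SE = (upper − lower) / (2t), with t = 2.080 at n = 22. The difference is the KD025 mean minus the placebo mean, with standard error √(SE₁² + SE₀²). This is unadjusted.

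**The case against.** **The table contains the control.** Placebo is randomised, selected by the same PASI rule and shown beside every KD025 arm. A reader might infer from the per-arm layout that the trial cannot separate KD025 from placebo response or regression to the mean, or that it amounts to five uncontrolled before-after series. The documents do not support that: step 7 recovers an unadjusted difference from the printed figures. This part of the objection stands. What is missing is a prespecified, baseline-adjusted estimate, not the information itself.

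**The objectives do not ask for it.** The primary objective names placebo as comparator; the PASI-change objectives do not. Protocol 12.1 makes testing conditional on its being appropriate, and this is a proof-of-principle Phase 2 study stopped early. So the SAP does not depart from the protocol here. It does for DLQI, where protocol 12.7 has ANCOVA and SAP 3.8.2 is descriptive; that is a separate discrepancy. Still, a placebo-controlled dose-finding trial needs the contrast to interpret PASI change, and the plan supplies one for PASI 75 and PGA.

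**Regression to the mean is small.** True over the assumed range, and it should not lead the argument. Placebo response is the larger reason to want the contrast, although the documents give no size for it on this scale.

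**No decision hangs on a within-arm CI.** Correct: neither document attaches a claim to one. The case rests on the missing estimate, not on a predicted misreading.

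**Conclusion.** The point holds in limited form. Neither document prespecifies a KD025-minus-placebo difference, interval or model for Week 16 PASI change or percent change. The primary analysis is unaffected. The change is worth making because these endpoints would otherwise be reported without a planned treatment effect, in a trial whose PASI 75 comparison has about 60% power at 22 per arm (46% at 18).

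How much the continuous comparison adds depends on the unknown effect size: about 49% power at 0.6 SD and 74% at 0.8 SD, with 22 per arm. A reader might set 97% against 60% and conclude that the most powerful comparison has been discarded. The 97% requires a normal, equal-SD model for a measure capped at 100%, and that model puts 9% to 14% of the KD025 arm above the cap under the assumed placebo means. It is an upper end, not an expectation. The regression-to-the-mean figures likewise rest on assumed PASI means, SDs and correlations.

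**What to change.** In SAP 3.8.2, for Week 16 PASI change and percent change, add the difference of each KD025 cohort from placebo with its 95% CI. Take it from an ANCOVA with treatment as fixed effect and baseline PASI as covariate, the form protocol 12.7 already uses. Keep the per-arm descriptive table, and add the contrast block to the by-visit PASI table in SAP section 4.

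State one missing-data rule for this analysis. At present SAP 3.1.2 brings in LOCF where it applies without naming an endpoint, and SAP 3.1.5 says that missing data are in general not imputed. Using observed values without comment would leave that conflict in place and, at the SAP's 17%, would drop about 4 of 22 subjects per arm (22 × 0.17 = 3.7). Whichever rule is chosen, reconcile it with both sections and report the number missing per arm.

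The cost is a few sentences and one table block, with no new data. The downside is 4 cohorts × 2 endpoints = 8 further unadjusted secondary comparisons, under the no-adjustment position already stated in protocol 12.7 and SAP 3.1.2.

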1 INTRODUCTION

Psoriasis is an autoimmune disease that affects many parts of the body but is primarily manifested in the skin. It affects 2% to 3% of the population globally, making it a very common inflammatory autoimmune disease. A number of biologic products have been approved for the treatment of moderate to severe chronic plaque psoriasis. However, there are still safety concerns and most of these products are parenterally administered. An oral agent such as KD025, which targets IL-17, could potentially provide an oral treatment option with an improved safety and efficacy profile.

This Statistical Analysis Plan (SAP) describes statistical procedures to be used for study KD025-211 as specified in the protocol (Amendment No. 2, 12-Mar-2019). The pharmacodynamic data will be analyzed and reported separately.

The SAP was written in accordance with the recommendations outlined in the International Conference on Harmonization (ICH) E9 Guideline entitled “Guidance for Industry: Statistical Principles for Clinical Trials” and the most recent ICH-E3 Guideline, entitled “Guidance for Industry: Structure and Content of Clinical Study Reports.”

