2.1.2 Secondary Objectives

- To assess changes in absolute PASI scores from baseline to Week 16
- To assess the mean percent change in PASI scores from baseline to Week 16
- To assess safety and tolerability of KD025
- To assess changes in Physicians Global Assessment (PGA)
- To assess changes in Dermatology Life Quality Index (DLQI)
- To assess changes in PASI scores from baseline to Week 48 for subjects receiving 48 weeks of KD025 treatment

- To evaluate the difference in PASI scores between Week 16 and Week 48 for subjects receiving KD025 for a total of 48 weeks

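### The SAP drops the protocol's PASI 50 endpoint and replaces the baseline-adjusted DLQI analysis with per-arm summaries, and declares neither change

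*SAP*

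**What the plan says.** **Protocol.** PASI 50 at Week 16 heads the list of secondary efficacy endpoints in section 5.5, in section 12.7 and in the synopsis. After specifying pairwise Fisher's exact tests against placebo for PASI 75, section 12.7 adds: "The number of subjects who reach PASI 50 at Week 16 will be analyzed similarly". For quality of life and global assessment it says: "Treatment group differences in DLQI and PGA changes from baseline to Week 16 will be assessed using an analysis of covariance (ANCOVA) model". The terms of that model are the treatment arm (fixed) and each subject's starting score (covariate). The synopsis repeats both commitments.

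**SAP.** Section 1 states: "This Statistical Analysis Plan (SAP) describes statistical procedures to be used for study KD025-211 as specified in the protocol", citing Amendment No. 2. Section 3.8.2 lists seven secondary endpoints, and PASI 50 is not among them. For DLQI it gives: "The descriptive statistics (n, mean, 95% CI) of DLQI changes from baseline to Week 16 will be summarized and tabulated by treatment". For PGA responders it says: "Use the same approach with primary endpoint analysis in section 3.8.1", so PGA keeps a Fisher comparison with placebo. In section 4, Table 3, the only PASI responder tables are for a 75% decrease, by Week 16 and by Week 48. The DLQI output is titled "DLQI score, change and % change from baseline by visit".

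**The concern.** A listed secondary endpoint and a named model disappear between protocol and SAP without comment. The SAP refers to the protocol as the source of its procedures, and the one change it explains is the early stop at 110 subjects (section 3.12).

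If the SAP is followed as written, PASI 50 is not reported at all, not even as counts. For DLQI a reader could rebuild an unadjusted difference from the per-arm statistics, but not the baseline-adjusted difference that the protocol planned. If PASI 50 is computed later, it will be without a pre-specified missing-data rule. A protocol-listed endpoint missing from the report also invites a question about selective reporting.

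**Working it through.** **1. Comparison of the texts**

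| Week 16 item | Protocol 12.7 | SAP 3.8.2 and Table 3 |
|---|---|---|
| PASI 50 | Pairwise Fisher test against placebo | Absent; no table |
| DLQI change | ANCOVA, treatment and baseline | n, mean, 95% CI per arm |
| PGA change | ANCOVA, treatment and baseline | Replaced by Fisher test on responders |

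ANCOVA is not mentioned anywhere in the SAP text, and no SAP section lists changes from the protocol. A possible cause, which is inference only: the list in 3.8.2 follows the secondary objectives in SAP 2.1.2 (for example "To assess changes in absolute PASI scores from baseline to Week 16"), leaving out safety and adding one Week 48 item. Those objectives never name PASI 50.

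The documents give no figure to reproduce on this point. The calculations below only size what is lost; the mismatch does not depend on them.

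**2. DLQI precision**

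Inputs: n = 22 per arm (SAP 2.2), five arms, two-sided 95%. The correlation ρ between baseline and Week 16 is not in the documents, so 0.3, 0.5 and 0.7 are assumed, with equal variances and complete data. Half-widths for a difference from placebo, in SD units:

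- Unadjusted change, pooled over five arms (105 df): t × √(2/n) × √(2(1−ρ))
- Unadjusted change, two arms only (42 df): same formula, larger t
- ANCOVA (104 df): t × √(2/n) × √(1−ρ²)

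Here √(2/22) = 0.3015, and t = 1.983, 2.018 and 1.983 respectively. For ρ = 0.5, ANCOVA gives 1.983 × 0.3015 × √0.75 = 0.518, and the pooled unadjusted interval gives 1.983 × 0.3015 × 1 = 0.598. The narrowing is 1 − 0.518/0.598 = 13%.

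| ρ | Unadjusted, 105 df | Unadjusted, 42 df | ANCOVA | Narrowing vs 105 df | Narrowing vs 42 df |
|---|---|---|---|---|---|
| 0.3 | 0.707 | 0.720 | 0.570 | 19% | 21% |
| 0.5 | 0.598 | 0.608 | 0.518 | 13% | 15% |
| 0.7 | 0.463 | 0.471 | 0.427 | 8% | 9% |

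**3. PASI 50 power**

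Exact enumeration of the two-sided Fisher test at p ≤ 0.05, summing the product of the two binomial probabilities over all significant tables. The placebo rates and the differences are assumptions. The 28-point row borrows the PASI 75 planning gap in SAP 3.12 (33% against 5%). The 17% missing is the planning figure in the same section, used as an illustration: counting missing as failure multiplies both rates by 0.83 at n = 22, and exclusion leaves 22 × 0.83 ≈ 18 per arm.

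| Scenario | Placebo 10% | 15% | 20% |
|---|---|---|---|
| True size, no effect | 1.4% | 2.2% | 2.4% |
| +40 points, 22 per arm | 79% | 73% | 69% |
| +30 points, 22 per arm | 55% | 48% | 43% |
| +28 points, 22 per arm | 49% | 43% | 38% |
| +40 points, 17% missing as failure | 66% | 59% | 54.5% |
| +40 points, 17% excluded (18 per arm) | 67% | 63% | 61% |

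The last two rows differ, so the rule has to be named.

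**4. Cost in false positives**

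Restoring both analyses adds four Fisher contrasts and four ANCOVA contrasts. With no effect anywhere, the expected number of false positives is 4 × 0.0144 + 4 × 0.05 = 0.26 to 4 × 0.0242 + 4 × 0.05 = 0.30. This comes on top of the eight Fisher tests already planned for PASI 75 and PGA.

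**The case against.** Protocol 12 and 12.7 defer the complete and further details of analysis to the SAP, hypothesis testing is conditional on being appropriate (protocol 12.1), and the trial is exploratory and stopped early. One could therefore read the SAP as the governing text and the reduction as a reasonable choice. The deferral covers elaboration. It does not extend to silently removing a listed endpoint or a named model, least of all in a SAP that says it follows the protocol. Early stopping also does not explain why Fisher tests stay for PASI 75 and PGA while PASI 50 goes.

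Four narrower points stand:

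- **Missing data.** The SAP itself is not uniform. Section 3.1.5 leaves missing subjects out of percentages unless otherwise specified, 3.1.2 allows LOCF when applicable, and the failure rule in 3.8.1 is worded only for the 75% decrease. A restored PASI 50 analysis needs an explicit rule, and so does the DLQI model. LOCF was not included in the power figures.
- **PGA.** Appendix C of the protocol rates PGA relative to baseline, so a change score with a baseline covariate has no clear meaning, and the responder analysis matches the protocol's own PGA endpoint. The substitution is defensible, though unexplained.
- **Size.** The correlations, placebo rates and differences are assumed. At the only gap the documents use for planning, 28 points, power is 38-49%.
- **Remedy.** A declared and reasoned change would also remove the contradiction.

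**Conclusion.** The concern holds. PASI 50 and its pairwise Fisher test are missing from the SAP, the DLQI ANCOVA has become per-arm description, and neither change is declared. This rests on the texts alone. The primary analysis is untouched, and the protocol still records both analyses, so the defect is an undeclared difference that should be corrected. Under the stated assumptions, what is lost is 8-19% of interval width for a DLQI difference, and a PASI 50 comparison with moderate power for large effects and low power at about 30 points or less.

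**What to change.** In SAP 3.8.2 and section 4, Table 3:

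1. Restore PASI 50 at Week 16 with pairwise Fisher tests against placebo, and add its table. For consistency with SAP 3.8.1, count a missing Week 16 score as failure, and state that this differs from the exclusion rule in protocol 12.1.
2. Restore the ANCOVA of Week 16 DLQI change with treatment and baseline DLQI. Protocol 12.7 names no contrasts, so add that the adjusted difference from placebo with 95% CI will be given for each dose. State the missing-data rule; the default in protocol 12.1 and SAP 3.1.5 is no imputation.
3. Add one sentence on why the PGA-change ANCOVA is replaced by the responder comparison.
4. Label these p-values nominal.

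If item 1 or 2 is not restored, declare it as a change from the protocol with the reason.

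The cost is SAP wording, one table and one standard model. PASI and DLQI are already scheduled at baseline and Week 16 (protocol Table 1-1). The added false-positive expectation of about 0.26-0.30 is why the nominal label is needed.
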